2 SYNOPSIS

Sponsor: Aldeyra Therapeutics, Inc.
Name of Finished Product: ADX-102
Name of Active Ingredient: ADX-102 Ophthalmic Drops (0.5%) and ADX-102 Ophthalmic Drops (0.1%)
Protocol Title: A Multi-Center, Double-Masked, Randomized, Vehicle-Controlled, Phase 2b Evaluation of the Onset and Duration of ADX-102 Ophthalmic Drops (0.5% and 0.1%) Compared to Vehicle of ADX-102 Ophthalmic Drops in the Conjunctival Allergen Challenge (Ora-CAC®) Model of Acute Allergic Conjunctivitis
Protocol Number: ADX-102-AC-004
Investigator: Multi-Center
Study Phase of Development: 2b
Objectives: To evaluate the efficacy of ADX-102 ophthalmic drops (0.5% and 0.1%) compared to vehicle of ADX-102 ophthalmic drops for the treatment of the signs and symptoms of acute allergic conjunctivitis.
Methodology: Structure: Multi-center, double-masked, randomized, vehicle-controlled, Phase 2b study to evaluate the efficacy of ADX-102 ophthalmic drops (0.5% and 0.1%) compared to vehicle of ADX-102 ophthalmic drops for the treatment of the signs and symptoms of acute allergic conjunctivitis.
Duration: This study consists of 4 office visits over a period of approximately 5 weeks. Screening Period: Screening will be approximately 3 weeks in duration. At Visit 1, subjects will undergo an allergen titration using an allergen they had a positive reaction to on their skin test. Subjects who elicit a positive reaction post-CAC will undergo the confirmation CAC at Visit 2 using the same allergen they qualified with at Visit 1. Treatment Period: Treatment will begin at Visit 3 after subjects are randomized. At this visit, subjects will receive an in-office dose of the treatment that they were randomized to receive. Subjects will receive 1 additional dose at Visit 4.
Summary of Visit Schedule: 
Visit 1 (Day -21 ± 3): Screening/Titration CACVisit 2 (Day -14 ± 3): Confirmation CACVisit 3 (Day 1): Enrollment/Randomization/ 1-Hour (+5 Minutes) Duration of Action CACVisit 4 (Day 15 ± 3): 10-Minutes Onset of Action CAC
Measures Taken to Reduce Bias: Randomization will be used to avoid bias in the assignment of subjects to investigational product, to increase the likelihood that known and unknown subject attributes (e.g., demographics and baseline characteristics) are evenly balanced across treatment groups, and to enhance the validity of statistical comparisons across treatment groups. In addition, randomization will be stratified by average post-CAC itching scores [REDACTED] at baseline (Visit 2) to ensure balance for the primary endpoint of ocular

Sponsor: Aldeyra Therapeutics, Inc.
Name of Finished Product: ADX-102
Name of Active Ingredient: ADX-102 Ophthalmic Drops (0.5%) and ADX-102 Ophthalmic Drops (0.1%)
Protocol Title: A Multi-Center, Double-Masked, Randomized, Vehicle-Controlled, Phase 2b Evaluation of the Onset and Duration of ADX-102 Ophthalmic Drops (0.5% and 0.1%) Compared to Vehicle of ADX-102 Ophthalmic Drops in the Conjunctival Allergen Challenge (Ora-CAC®) Model of Acute Allergic Conjunctivitis
itching. Finally, masked treatment will be used to reduce potential of bias during data collection and evaluation of clinical endpoints.
Study Population Characteristics
Number of Subjects: Approximately 375 subjects will be screened in order to enroll approximately 150 subjects at up to 5 sites.
Diagnosis: Acute allergic conjunctivitis
Inclusion Criteria Each subject must:
1) be at least 18 years of age of either gender and any race; 2) provide written informed consent and sign the HIPAA form; 3) be willing and able to follow all instructions and attend all study visits; 4) have a positive history of ocular allergies and a positive skin test reaction to a [REDACTED] allergen [REDACTED] as confirmed by an allergic skin test within the [REDACTED]; 5) be able and willing to avoid all disallowed medications for the appropriate washout period and during the study (see exclusion 6); 6) be able and willing to discontinue wearing contact lenses for at least 72 hours prior to and during the study trial period; 7) have a calculated visual acuity of 0.7 logMAR or better in each eye as measured using an ETDRS chart; 8) (for females capable of becoming pregnant) agree to have urine pregnancy testing performed at screening (must be negative) and exit visit; must not be lactating; and must agree to use a medically acceptable form of birth control ¹ throughout the study duration and for at least 14 days prior to the instillation of investigational product (Visit 3). Women considered capable of becoming pregnant include all females who have experienced menarche and have not experienced menopause (as defined by amenorrhea for greater than 12 consecutive months) or have not undergone successful surgical sterilization (hysterectomy, bilateral tubal ligation, or bilateral oophorectomy); 9) have a positive bilateral CAC reaction [REDACTED] within 10 [REDACTED]

¹Acceptable forms of birth control are spermicide with barrier, oral contraceptive, injectable or implantable method of contraception, transdermal contraceptive, intrauterine device, or surgical sterilization of partner. For non-sexually active females, abstinence will be considered an acceptable form of birth control.

Sponsor: Aldeyra Therapeutics, Inc.
Name of Finished Product: ADX-102
Name of Active Ingredient: ADX-102 Ophthalmic Drops (0.5%) and ADX-102 Ophthalmic Drops (0.1%)
Protocol Title: A Multi-Center, Double-Masked, Randomized, Vehicle-Controlled, Phase 2b Evaluation of the Onset and Duration of ADX-102 Ophthalmic Drops (0.5% and 0.1%) Compared to Vehicle of ADX-102 Ophthalmic Drops in the Conjunctival Allergen Challenge (Ora-CAC®) Model of Acute Allergic Conjunctivitis
(±2) minutes of instillation of the last titration of allergen at Visit 1; 10) have a positive bilateral CAC reaction [REDACTED] for at least two out of the first three time points ¹ following the challenge at Visit 2.
Exclusion Criteria Each subject may not: 
1) have known contraindications or sensitivities to the use of the investigational product or any of its components;2) have any ocular condition that, in the opinion of the investigator, could affect the subject's safety or trial parameters (including but not limited to narrow angle glaucoma, clinically significant blepharitis, follicular conjunctivitis, iritis, pterygium or a diagnosis of dry eye);3) have had ocular surgical intervention within three (3) months prior to Visit 1 or during the study and/or a history of refractive surgery within the past six (6) months;4) have a known history of retinal detachment, diabetic retinopathy, or active retinal disease;5) have the presence of an active ocular infection (bacterial, viral or fungal) or positive history of an ocular herpetic infection at any visit;6) use any of the following disallowed medications during the period indicated prior to Visit 1 and during the study:
72 hours
• systemic or ocular H₁ antihistamine, H₁ antihistamine/mast cell stabilizers, H₁ antihistamine-vasoconstrictor drug combinations7 days
• decongestants• monoamine oxidase inhibitors• all other topical ophthalmic preparations (including artificial tears)• lid scrubs• topical prostaglandins or prostaglandin derivatives• ocular, topical, or systemic nonsteroidal anti-inflammatory drugs (NSAIDs)14 days
• inhaled, ocular, topical, or systemic corticosteroids or mast cell stabilizers45 days
• depo-corticosteroids

¹ not necessarily at the same time point

Sponsor: Aldeyra Therapeutics, Inc.
Name of Finished Product: ADX-102
Name of Active Ingredient: ADX-102 Ophthalmic Drops (0.5%) and ADX-102 Ophthalmic Drops (0.1%)
Protocol Title: A Multi-Center, Double-Masked, Randomized, Vehicle-Controlled, Phase 2b Evaluation of the Onset and Duration of ADX-102 Ophthalmic Drops (0.5% and 0.1%) Compared to Vehicle of ADX-102 Ophthalmic Drops in the Conjunctival Allergen Challenge (Ora-CAC®) Model of Acute Allergic Conjunctivitis

2 months
 
immunotherapeutic agents: treatment must have been maintained steadily for at least 2 months; neither the immunotherapeutic agent nor its dosage may change during the clinical trial. 
Note: Currently marketed over-the-counter anti-allergy eye drops (i.e. anti-histamine/ vasoconstrictor combination products such as Visine®-A®) may be administered by trained study personnel to subjects at the end of Visits 1, 2, 3, and 4, after all evaluations are completed.
 
7) have any significant illness (e.g. any autoimmune disease requiring therapy, severe cardiovascular disease [including arrhythmias] the investigator feels could be expected to interfere with the subject's health or with the study parameters and/or put the subject at any unnecessary risk (includes but is not limited to: poorly controlled hypertension or poorly controlled diabetes, a history of status asthmaticus, organ transplants, a known history of persistent moderate or severe asthma, or a known history of moderate to severe allergic asthmatic reactions to any of the study allergens;
 
8) manifest signs or symptoms of clinically active allergic conjunctivitis in either eye at the start of Visits 1, 2, or 3 [REDACTED] [REDACTED] [REDACTED];
 
9) have a history of glaucoma, ocular hypertension or an intraocular pressure (IOP) that is greater than 24 mmHg at Visit 1;
 
10) have planned surgery (ocular or systemic) during the trial period or within 30 days after;
 
11) have used an investigational drug or medical device within 30 days of the study or be concurrently enrolled in another investigational product trial;
 
12) be a female who is currently pregnant, planning a pregnancy, lactating, not using a medically acceptable form of birth control throughout the study duration and for 14 days prior to the installation of investigational product, or has a positive urine pregnancy test at Visit 1.

Test Product, Dose and Mode of Administration, Batch Number:

ADX-102 Ophthalmic Drops (0.5%)ADX-102 Ophthalmic Drops (0.1%)
Reference Therapy, Dose and Mode of Administration, Batch Number:

Vehicle of ADX-102 Ophthalmic Drops
Criteria for Evaluation:
Efficacy Measures:
Primary:

Ocular itching evaluated by the subject at 10(±1), 15(±1), and 20(±1) minutes post-CAC at Visits 3 and 4 (0-4 scale, allowing half unit increments)

Sponsor: Aldeyra Therapeutics, Inc.

Name of Finished Product: ADX-102

Name of Active Ingredient: ADX-102 Ophthalmic Drops (0.5%) and ADX-102 Ophthalmic Drops (0.1%)

Protocol Title: A Multi-Center, Double-Masked, Randomized, Vehicle-Controlled, Phase 2b Evaluation of the Onset and Duration of ADX-102 Ophthalmic Drops (0.5% and 0.1%) Compared to Vehicle of ADX-102 Ophthalmic Drops in the Conjunctival Allergen Challenge (Ora-CAC®) Model of Acute Allergic Conjunctivitis

Safety Measures:

- Adverse Events (reported, elicited and observed)
- Visual Acuity at Distance Utilizing an ETDRS chart
- Slit-lamp Biomicroscopy
- Intraocular Pressure
- Dilated Fundoscopy

General Statistical Methods and Types of Analyses

Approximately 150 subjects will be randomized at Visit 3, or approximately 50 subjects per treatment arm.

Quantitative variables will be summarized using descriptive statistics, that is, number of observations, mean, standard deviation, median, minimum, and maximum. Qualitative variables will be summarized using counts and percentages. Statistical testing will be performed at a two-sided significance level of alpha = 0.05. For all analyses, comparisons will be made between each dose of ADX-102 Ophthalmic Drops and vehicle.

[figure not shown]
[figure not shown]
[figure not shown]

Sponsor: Aldeyra Therapeutics, Inc.

Name of Finished Product: ADX-102

Name of Active Ingredient: ADX-102 Ophthalmic Drops (0.5%) and ADX-102 Ophthalmic Drops (0.1%)

Protocol Title: A Multi-Center, Double-Masked, Randomized, Vehicle-Controlled, Phase 2b Evaluation of the Onset and Duration of ADX-102 Ophthalmic Drops (0.5% and 0.1%) Compared to Vehicle of ADX-102 Ophthalmic Drops in the Conjunctival Allergen Challenge (Ora-CAC®) Model of Acute Allergic Conjunctivitis

The primary efficacy variable is measured at Visit 3 (1 hour post treatment) and Visit 4 (10 minutes post treatment).
   

The primary safety variable is the incidence of subjects with any adverse event during the entire study. The percentage of subjects with specific treatment-emergent adverse events will be summarized for each treatment group. A treatment-emergent adverse event (TEAE) is defined as any event not present prior to the initiation of the treatments or any event already present that worsens in either intensity or frequency following exposure to the treatments. Incidence will be tabulated by Medical Dictionary for Regulatory Activities (MedDRA) System Organ Class and preferred term within each system organ class. The secondary safety variables of visual acuity, slit lamp biomicroscopy, IOP, and dilated fundoscopy will be summarized descriptively.

Summary of Known and Potential Risks and Benefits to Human Subjects
 
Refer to Investigator's Brochure.

TABLE OF CONTENTS

1 CLINICAL TRIAL PROTOCOL: ADX-102-AC-004	1
2 SYNOPSIS.....	3
TABLE OF CONTENTS	9
List of Abbreviations	12
3 INTRODUCTION	14
4 STUDY OBJECTIVES.....	15
5 CLINICAL HYPOTHESES	15
6 OVERALL STUDY DESIGN	15
7 STUDY POPULATION.....	15
7.1 Number of Subjects (approximate)	15
7.2 Study Population Characteristics	16
7.3 inclusion Criteria	16
7.4 Exclusion Criteria.....	17
7.5 Withdrawal Criteria (if applicable).....	18
8 STUDY MEASURES	19
8.1 Efficacy Measures	19
8.1.1 Primary Efficacy Measure(s).....	19
8.1.3 Criteria for Effectiveness.....	19
8.2 Safety Measures	19
9 STUDY MATERIALS.....	20
9.1 Study Treatment(s)	20
9.1.1 Study Treatment(s)/ Formulation(s)	20
9.1.2 Instructions for Use and Administration	20
9.2 Other Study Supplies	20
10 STUDY METHODS AND PROCEDURES.....	21
10.1 Subject Entry Procedures	21
10.1.1 Overview	21
10.1.2 Informed Consent	21
10.1.3 Washout Intervals	21
10.1.4 Procedures for Final Study Entry	22
10.1.5 Methods for Assignment to Treatment Groups:.....	22
10.2 Concurrent Therapies	22
10.2.1 Prohibited Medications/Treatments	23
10.2.2 Escape Medications	23
10.2.3 Special Diet or Activities	23
10.3 Examination Procedures	23
10.3.1 Procedures to be Performed at Each Study Visit with Regard to Study Objective(s)	23
10.4 Schedule of Visits, Measurements and Dosing	28
10.4.1 Scheduled Visits	28
10.4.2 Unscheduled Visits.....	29

10.5 Compliance with Protocol.....	29
10.6 Subject Disposition.....	29
10.6.1 Completed Subjects	29
10.6.2 Discontinued Subjects	29
10.7 Study Termination.....	30
10.8 STUDY Duration.....	30
10.9 Monitoring and Quality Assurance.....	30

CRF	case report form
CRO	contract research organization
DHHS	Department of Health and Human Services
ECG	electrocardiogram
ERC	ethical review committee
ETDRS	Early Treatment of Diabetic Retinopathy Study
FDA	Food and Drug Administration
GCP	Good Clinical Practice
HIPAA	Health Information Portability and Accountability Act
IB	investigators' brochure
ICF	informed consent form
ICH	International Conference on Harmonisation
IgE	immunoglobulin-E
IND	investigational new drug application
IOP	intraocular pressure
IP	investigational product
IRB	institutional/independent review board
ITT	intent to treat
LASIK	laser in situ keratomileusis
LOCF	last observation carried forward
logMAR	logarithm of the minimum angle of resolution

LS	least squares
MCMC	Markov Chain Monte Carlo
MedDRA	Medical Dictionary for Regulatory Activities
MI	multiple imputation
mmHg	millimeters of mercury
NCS	not clinically significant
NDA	new drug application
NSAID	nonsteroidal anti-inflammatory drug
OD	right eye
Ora-CAC®	conjunctival allergen challenge
OS	left eye
OU	both eyes
OTC	over the counter
PHI	protected health information
PP	per protocol
ROPI	Report of Prior Investigations
SAE	serious adverse event
SAP	statistical analysis plan
TEAE	treatment emergent adverse event
VA	visual acuity

3 INTRODUCTION

[figure not shown]
[REDACTED]

[REDACTED]

[REDACTED]

[REDACTED]

[REDACTED]

4 STUDY OBJECTIVES

To evaluate the efficacy of ADX-102 ophthalmic drops (0.5% and 0.1%) compared to vehicle of ADX-102 ophthalmic drops for the treatment of the signs and symptoms of acute allergic conjunctivitis.

5 CLINICAL HYPOTHESES

It is hypothesized that at least one concentration of ADX-102 ophthalmic drops will be more effective than vehicle of ADX-102 in the treatment of the signs and symptoms of acute allergic conjunctivitis.

6 OVERALL STUDY DESIGN

This is a multi-center, double-masked, randomized, vehicle-controlled, phase 2b study evaluating the efficacy of ADX-102 ophthalmic drops (0.5% and 0.1%) compared to vehicle of ADX-102 ophthalmic drops for the treatment of the signs and symptoms of acute allergic conjunctivitis.

The trial will comprise of 4 office visits over a period of approximately 5 weeks. Visits 1 and 2 will be used to select a subject population that responds reproducibly to two CACs administered approximately 7 days apart. Subjects who meet the entry criteria for itching and redness response to CAC at Visits 1 and 2 will be randomized (1:1:1) at Visit 3 (Day 1, Enrollment/Randomization) to receive either ADX-102 ophthalmic drops (0.5%), ADX-102 ophthalmic drops (0.1%), or vehicle of ADX-102 ophthalmic drops bilaterally. Subjects will undergo the 1-hour (+5 minutes) duration of action CAC from the time of their instillation. Subjects will return approximately 14 days later for Visit 4 (Day 15± 3, 10-Minutes Onset of Action CAC), at which time they will be treated with the same treatment they received at Visit 3 and challenged approximately 10 minutes after dosing. At Visit 4, final exit procedures will also be conducted and subjects will exit the study.

7 STUDY POPULATION

7.1 NUMBER OF SUBJECTS (APPROXIMATE)

Approximately 375 subjects will be screened in order to enroll approximately 150 subjects at up to 5 sites.

7.2 STUDY POPULATION CHARACTERISTICS

Subjects at least 18 years of age of either gender and any race, who meet all of the inclusion criteria and none of the exclusion criteria.

7.3 INCLUSION CRITERIA

Each subject must:

- 1) be at least 18 years of age of either gender and any race;
- 2) provide written informed consent and sign the HIPAA form;
- 3) be willing and able to follow all instructions and attend all study visits;
- 4) have a positive history of ocular allergies and a positive skin test reaction to a [REDACTED] allergen [REDACTED]
[REDACTED] as confirmed by an allergic skin test within the [REDACTED]
[REDACTED]
- 5) be able and willing to avoid all disallowed medications for the appropriate washout period and during the study (see exclusion 6);
- 6) be able and willing to discontinue wearing contact lenses for at least 72 hours prior to and during the study trial period;
- 7) have a calculated visual acuity of 0.7 logMAR or better in each eye as measured using an ETDRS chart;
- 8) (for females capable of becoming pregnant) agree to have urine pregnancy testing performed at screening (must be negative) and exit visit; must not be lactating; and must agree to use a medically acceptable form of birth control³ throughout the study duration and for at least 14 days prior to the instillation of investigational product (Visit 3). Women considered capable of becoming pregnant include all females who have experienced menarche and have not experienced menopause (as defined by amenorrhea for greater than 12 consecutive months) or have not undergone successful surgical sterilization (hysterectomy, bilateral tubal ligation, or bilateral oophorectomy);
- 9) have a positive bilateral CAC reaction [REDACTED]
[REDACTED] within 10 (± 2) minutes of instillation of the last titration of allergen at Visit 1;
- 10) have a positive bilateral CAC reaction [REDACTED]
[REDACTED] at least two out of the first three time points following the challenge at Visit 2.

³Acceptable forms of birth control are spermicide with barrier, oral contraceptive, injectable or implantable method of contraception, transdermal contraceptive, intrauterine device, or surgical sterilization of partner. For non-sexually active females, abstinence will be considered an acceptable form of birth control.

⁴ not necessarily at the same time point

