8 STUDY MEASURES

8.1 EFFICACY MEASURES

8.1.1 Primary Efficacy Measure(s)

- Ocular itching evaluated by the subject at 10(± 1), 15(± 1), 20(± 1) minutes post-CAC at Visits 3 and 4 (0-4 scale, allowing half unit increments)

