10.3.1.2 VISIT 2 (Day -14±3): Confirmation CAC

- *Update of Medical/Medication History*
- *Visual Acuity Utilizing an ETDRS Chart*: The Investigator should be notified if there is a clinically significant visual acuity decrease (defined as an increase of 0.22 or greater in logMAR score) from Visit 1.
- *Pre-CAC Ocular Allergic Signs and Symptoms Assessment*: [REDACTED]
[REDACTED]
- *Slit Lamp Biomicroscopy*
- *Review of Inclusion/Exclusion Criteria*

- *Confirmation CAC:* [REDACTED]
- *Post-CAC Ocular Allergic Signs and Symptoms Assessment:* Assessment of itching will be made by the subject at 5(±1), 10(±1), 15(±1), 20(±1), 30(±1), and 60(±5) minutes following allergen challenge. Assessments of redness and chemosis will be graded by the Investigator and assessments of eyelid swelling, and tearing/watery eyes will be made by the subject at 10(±1), 15(±1), 20(±1), 30(±1), and 60(±5) minutes post-challenge (**Appendix 2**). If the subject fails to react positively [REDACTED] in both eyes in at least two out of the first three time points⁵ within the first 20-minute interval, he/she will be excluded from the study.
- [REDACTED]
- *Scheduling of Next Visit (Visit 3):* Subjects will be asked to return to the office 2 weeks later for Visit 3.

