12.4 CRITERIA FOR EFFICACY

This clinical study is designed to evaluate the efficacy of ADX-102 Ophthalmic Drops compared to vehicle in the prevention of ocular itching at each designated time point post-CAC at Visits 3 and 4.

[figure not shown]
To demonstrate the clinical effectiveness for ocular itching, ADX-102 Ophthalmic Drops will need to show clinical superiority over vehicle by at least 0.5 units of a 5 point scale for the 10(± 1), 15(± 1) and 20(± 1) minutes post-CAC time points within a visit, and at least 1 unit for the majority [REDACTED] of the same three post-CAC time points within a visit for each treatment comparison. ADX-102 Ophthalmic Drops will also need to show statistical superiority over vehicle at each of the three time points. The treatments will be tested against vehicle hierarchically, with the higher dose (0.5% ADX-102 Ophthalmic Drops) tested first and the lower dose (0.1% ADX-102 Ophthalmic Drops) tested conditional upon the higher dose showing statistical significance over vehicle.

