9.3 Definition of Baseline

For the primary efficacy variable (ocular itching scores at 10(± 1), 15(± 1), and 20(± 1) minutes post-CAC), baseline will refer to the time-relevant measure at Visit 2 (e.g., ocular itching at 10 minutes post-CAC at Visit 2 will be the baseline for ocular itching at 10 minutes post-CAC at Visits 3 and 4).

For all safety variables, baseline is defined as the last measurement prior to the first dose of study medication. Change from baseline will be calculated as follow-up visit minus baseline visit.

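### Does the Visit 2 qualification rule need to name 10, 15 and 20 minutes so that it matches the primary itching times?

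*Protocol*

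**What the plan says.** Inclusion criterion 10 asks for a positive bilateral reaction at "at least two out of the first three time points following the challenge at Visit 2" (Protocol 7.3). The synopsis has the same rule: "for at least two out of the first three time points". In both places the footnote says only that the reactions need not coincide in time. Protocol 10.3.1.2 repeats the rule with a time limit: a subject who does not react often enough "within the first 20-minute interval, he/she will be excluded from the study".

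Protocol 6 shows that the reaction has two components: "Subjects who meet the entry criteria for itching and redness response to CAC at Visits 1 and 2 will be randomized". Their Visit 2 schedules start at different times. For itching, "Assessment of itching will be made by the subject at 5(±1), 10(±1), 15(±1), 20(±1), 30(±1), and 60(±5) minutes following allergen challenge". Redness is graded at 10, 15, 20, 30 and 60 minutes.

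The primary measure is "Ocular itching evaluated by the subject at 10(± 1), 15(± 1), 20(± 1) minutes post-CAC at Visits 3 and 4" (Protocol 8.1.1). SAP 9.3 ties its baseline to the same clock times: "baseline will refer to the time-relevant measure at Visit 2". Protocol 12.4 asks for a difference from vehicle of at least 0.5 unit at all three times and "at least 1 unit for the majority" of them, with statistical superiority at each.

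**The concern.** Counted literally, one phrase yields two sets of minutes: 5, 10 and 15 for itching, and 10, 15 and 20 for redness. The 20-minute limit does not decide the itching set, because four itching readings fall within it. Up to five sites could therefore screen on different windows from the same sentence.

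The literal itching set also differs from the primary set. A subject could enter after itching enough at 5 and 10 minutes only, and so be below threshold at two of the three times on which success is judged. If such subjects itch little at those times again at Visits 3 and 4, there is less itch for the drug to remove, and the 0.5-unit and 1-unit requirements become harder to meet. What would be at stake is sensitivity and uniform screening, not bias.

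**Working it through.** **Times, side by side**

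| Item | Minutes | Source |
|---|---|---|
| Itching readings at Visit 2 | 5, 10, 15, 20, 30, 60 | Protocol 10.3.1.2 |
| Redness readings at Visit 2 | 10, 15, 20, 30, 60 | Protocol 10.3.1.2 |
| Literal first three, itching | 5, 10, 15 | by counting |
| Literal first three, redness | 10, 15, 20 | by counting |
| First three times common to both | 10, 15, 20 | by counting |
| Primary itching times and their baseline | 10, 15, 20 | Protocol 8.1.1, SAP 9.3 |

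The times common to both components end at 20 minutes, as the limit in Protocol 10.3.1.2 does. A literal itching set would end at 15, and the limit would then do no work for itching. This favors 10, 15 and 20 without proving it.

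**Itching patterns.** Four readings, each positive or negative, give 2^4 = 16 patterns.

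- Two of 5, 10, 15 admits 8.
- Two of 10, 15, 20 admits 8.
- Any two of the four admits 11.

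The first two rules share 6 patterns, so they disagree on (8 - 6) + (8 - 6) = 4. The literal rule alone admits {5, 10} and {5, 15}, which are positive at one primary time. It rejects {10, 20} and {15, 20}, which are positive at two. Every literal qualifier is positive at one or more primary times. These are counts of logical patterns, not shares of subjects.

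**Chance of meeting the 0.5-unit and 1-unit requirements.** The plan shows no power figure to reproduce. The documents supply 50 subjects per arm and the success rule. Everything else is assumed: SD 0.9, correlation 0.8 between times, usual itch 2.5, drug effect a fixed proportion r of the itch score, and a fraction f of subjects with a low score L.

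- Standard error of a difference: 0.9 × sqrt(2/50) = 0.18. Since 0.5/0.18 = 2.78 exceeds 1.96, the significance requirement adds nothing here.
- Literal rule, with all affected subjects low at 15 and 20: mean difference 2.5r at 10 minutes and ((1 - f) × 2.5 + f × L) × r at 15 and 20.
- Aligned rule, with each affected subject low at one primary time, spread evenly: ((1 - f/3) × 2.5 + (f/3) × L) × r at each time.
- Example, r = 0.5, L = 1.0, f = 10%: literal (0.9 × 2.5 + 0.1 × 1.0) × 0.5 = 1.175 at 15 and 20; aligned (0.9667 × 2.5 + 0.0333 × 1.0) × 0.5 = 1.225 at all three.

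Results from 1,000,000 draws, literal against aligned:

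| r | L | f = 10% | f = 20% |
|---|---|---|---|
| 0.5 | 1.0 | 87.8 vs 90.8% | 78.9 vs 88.1% |
| 0.5 | 2.0 | 91.6 vs 92.3% | 89.9 vs 91.6% |
| 0.4 | 1.0 | 40.5 vs 45.3% | 30.6 vs 40.7% |
| 0.4 | 2.0 | 46.9 vs 48.5% | 43.7 vs 46.9% |

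The gain is about 1 to 10 points for f of 10 to 20%, and 0.4 to 2.4 points for f of 5%.

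**How much depends on the assumptions**

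- Additive drug effect with no floor: the means no longer depend on the entry rule. Success is 92.9% at a difference of 1.25 units and 50.0% at 1.0 under either rule, a gain of 0.
- Only half of the affected subjects still low at Visits 3 and 4: the gain for f of 10 to 20% falls to about 0.4 to 4.8 points.
- Affected subjects split evenly between {5, 10} and {5, 15}: 0.7 to 8.5 points.

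The entry threshold is redacted, so L = 1.0, which produces the largest figures, cannot be checked.

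**The case for a change.** The best case for a change is that it costs almost nothing: wording in three places and no new measurement. The redactions also look more like score thresholds than minutes. They come directly after the mention of a positive reaction, and in criterion 9 a redaction in the same position is followed by visible minutes. The visible footnotes add no times. On that view the minutes really are absent, and sites are left to choose.

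Part of this stands. The visible wording is ambiguous for itching, and the 20-minute limit does not remove the ambiguity. But the guess about the redactions is inference. The footnote attached to the rule in Protocol 10.3.1.2 is not shown, and the examination procedures in Appendix 2 are redacted. Text withheld from the public copy cannot be counted as missing from the plan, and the documents give no sign that sites would differ.

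Naming the minutes and choosing 10, 15 and 20 are also separate steps. The first is clarification. The second is a preference: nothing in either document requires the qualifying times to equal the endpoint times.

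**Conclusion.** No change to the plan follows. What remains is a point of wording that the unredacted protocol may already settle, with a sensible reading available in the visible text: the three times shared by itching and redness, which end at 20 minutes and coincide with the primary times.

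The comparison is sound on any reading. Eligibility is fixed before randomization and is the same in every arm, and randomization is stratified by the average Visit 2 itching score (Protocol 10.1.5). The rule affects who is enrolled and how high the time-matched baseline is. It does not favor one arm.

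No effect on power can be established from the documents. The range of about 1 to 10 points requires a proportional drug effect, an unsourced share of affected subjects, an unsourced low score and low itch that persists to Visits 3 and 4. The range extends to zero when the effect is additive. The conclusion would need another look only if the full text were shown to name no minutes and sites were found to have screened on different windows. Even then the issue would be consistency of enrollment, not validity of the treatment comparison.
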